Increasing evidence shows that transcutaneous auricular nerve stimulation (taVNS) can significantly reduce multiple symptoms of stress disorder including depression, fatigue, cognitive impairment, anxiety, psychomotor retardation, sleep disturbance (Kong et al, 2018; Aranow et al 2020). One of the collaborators in this study [name] has developed and patented RAVANS, a type of taVNS, which synchronizes stimulation to the respiratory cycle, modulate vagal systems and optimize stimulations (Napadow et al 2012; Garcia et al, 2017; Yakunina et al 2017). RAVANS has been shown beneficial effect in pain management (Napadow et al 2012; Garcia et al, 2017).

In this study, we will conduct a randomized, double blinded, sham-controlled pilot study to **explore the effect of RAVANS on the symptoms in individuals diagnosed with PTLDS using psychometric measurement, function and cognitive test, and serum biomarkers.**

II. SPECIFIC AIMS

Aim 1. Determine if Respiratory-gated Auricular Vagal Afferent Nerve Stimulation (RAVANS) can improve symptoms of Post-Treatment Lyme Disease Syndrome (PTLDS)

Aim 2: Determine if RAVANS reduces inflammation as measured by serum biomarkers (IL6, IL-10, TNF, IL-1 β) after RAVANS treatment in people with PTLDS

Aim3: Determine if inflammation as measured by serum biomarkers (IL-6, IL-10, TNF, IL-1 β) correlates with severity of PTLDS.

INVESTIGATORS:

[name] [name], PhD, Spaulding Rehabilitation Hospital

Principal Investigator, recruitment, screening and consenting, data collection and analysis

[name], Spaulding Rehabilitation Hospital

*Medical Monitor

[name], Massachusetts General Hospital

Co-investigator, recruitment, data analysis

[name], LicAc, Massachusetts General Hospital

Co-investigator, RAVANS inventor, RAVANS technical support, data analysis,

*Responsibilities of the Medical Monitor

The medical monitor is required to review all unanticipated problems involving risk to subjects or others, serious adverse events and all subject deaths associated with the protocol and provide an unbiased written report of the event. At a minimum, the medical monitor must comment on the outcomes of the event or problem and in case of a serious adverse event or death, comment on the relationship to participation in the study. The medical monitor must also indicate whether he concurs with the details of the report provided by the principal investigator.

III. SUBJECT SELECTION

Inclusion criteria include:

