- 1) Adults of all genders \geq 18 years
- 2) History of Lyme disease treated with antibiotics, and current PTLDS diagnosed by a physician
3. Evidence of past *B. burgdorferi* infection based on positive results from both enzyme immunoassay and Western blot testing.
- 4) Ability to provide informed consent,

5) Willing to maintain current PTLDS treatment regimen during participation in the study (if on long-term antibiotics or supplements for PTLDS management).

Exclusion criteria include:

- 1) History of other neurological disorder that in the judgement of the investigator could interfere with the treatment or the interpretation of the results (e.g., epilepsy, history of stroke, tumor, brain tissue damaging pathologies etc.).
- 2) Current psychotic disorder (e.g., schizophrenia).
- 3) Current acute illness or infection (e.g. cold or flu).
- 4) Current or past history of psychiatric illness; PTSD, depression and anxiety are exclusion criteria only if the conditions are so severe as to have required hospitalization in the past 5 years.
- 5) History of asystole
- 6) History of recurrent vaso-vagal syncope
- 7) Bradycardia defined as resting heart rate <50bpm
- 8) Implanted electronic device (e.g., pacemaker, neurostimulator)
- 9) Use of immunosuppressive medication such as prednisone, TNF medications within 2 weeks of the visit or anticipated use during the study
- 10) Current use of anti-inflammatory steroid use
- 11) Pregnancy

The target population is 48 individuals \geq 18 years of age who have been diagnosed with PTLDS. All subjects receiving outpatient care at SRH may be eligible for the study and will be sought to participate through publicity flyers. The safety of RAVANS in the pediatric and pregnant population has not been assessed and therefore pregnant women will be excluded. Women of child-bearing potential will be required to take a urine pregnancy test for both study visits.

IV. SUBJECT ENROLLMENT

Potential subjects will be identified by the following sources:

- 1) Clinicians may refer their patients with PTLDS to the study. We will provide the clinicians with study information sheets and flyers. Prospective subjects will be encouraged to contact the study co-investigators. Flyers will be posted in the outpatient clinic area.
- 2) Will obtain the patient's names via medical records and RPDR

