- 3) Will use the Mass General Brigham Research Invitations procedures for recruitment. We will send prospective subjects a letter via the Research Invitation Program.

At the first point of contact (usually a phone call), a study co-investigator will provide a description of the study, discuss study procedure, and administer a phone screening questionnaire. Once the phone screening process is complete, the information gathered by the co-investigator will be taken to the PI of the study for further review. Once the PI agrees that the subject is thus far eligible, the subject will be scheduled their first visit. Consent form will be mailed to the subject ahead of time.

Informed consent will be obtained by a license physician, PI [name] [name] at SRH. The subject will meet with [name]. The test procedures will be described, and the testing equipment will be shown to the subject. [name] will clearly explain all the procedures and risks of the testing outlined in the consent form. The subject will be given an hour to consider their decision and will be encouraged to ask questions, both during the initial phone interview and throughout the study. [name] will answer any questions regarding the study at the time of the informed consent process. Once enrolled, the subject may pause or terminate his/her participation at any time during the study.

Participants will be randomized to receive active or sham RAVANS treatment 3 times per week for 2 weeks through a randomization approach with blocks of 4 (given the sample size of 48 participants, this would give 12 blocks of 4). Randomization of subjects will be blocked based on the 2 treatment options available.

V. STUDY PROCEDURES

First visit: consent, blood drawn, baseline evaluation, first RAVANS/Sham treatment

During this first visit, we will conduct the consent process. Participants that provide informed consent will be interviewed to complete inclusion/exclusion check list. The qualified subjects will be included in the study. They will complete the questionnaires (Demographic Data Questionnaire, Functional Comorbidity Index, Horowitz Lyme-MSIDS, Sedentary Behaviors Questionnaire, Fatigue Symptom Inventory, Brief Pain Inventory, Vulnerability questionnaire, Beck Depression Inventory, Beck Anxiety Inventory, Pittsburgh Sleep Quality Index), functional test (Timed Up and Go, 4 meter usually walking speed, NIH Toolbox cognitive battery), blood drawn and they will receive 1st RAVANS or sham treatment.

Blood test

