Respiratory-gated auricular vagus afferent nerve stimulation (RAVANS) will be performed with electrodes attached to the surface of the auricle. A small current will be delivered with a safe battery-powered portable stimulator, also used in other Partners IRB protocols (IRB#2016P000210). Current amplitude will be set between the sensitivity threshold and the pain threshold for each subject, to ensure non-noxious stimulation. Respiratory gating for stimulation will require real-time evaluation of the respiratory cycle, as described below.

For RAVANS setup, electrodes will be placed on the auricle of the left ear. Electrical stimulation to these electrodes will be provided by a current-constant stimulator (Cala

Health Inc, Burlingame, CA). Stimulation will be gated to the subject's own breathing, at a 1-second delay after peak inhalation (i.e. during exhalation.)

Sham stimulation: RAVANS device has a sham control mode on it. For sham stimulation, the device setup will be the same but no electrical current will be passed. Participant will be given instruction to use Mode 1(Active RAVANS) or Mode 2 (Sham stimulation) according to randomization. However, the participant would not know the setting of Mode 1 or Mode 2.

[figure not shown]

Figure 1: Setup of RAVANS: A. Electrode B. Placement of electrode on the auricle of the ear. C. Respiration belt and cables. D. Placement of respiration belt to gate the subject's breathing. E. Tablet to control the stimulation F. Cala stimulation program in the tablet

Assessments	Visit 1	Visits 2-5	Visit 6
DDQ	X		
FCI	X		
HL-MSIDS	X		X
SBQ	X		X
FSI	X		X

BPI	X		X
VQ	X		X
BDI	X		X
BAI	X		X
PSQI	X		X
Times Up and Go	X		X
4 meter Walk Speed	X		X
NIHTB-CB	X		X
Blood Drawn	X		X
RAVANS/ShamTreatment	X	X	X
Urine pregnancy test for women of child bearing potential	X		X
Approximate Time	4 hours	20 minutes per visit	4 hours

Visit 2-5:

Subjects will receive RAVANS or sham treatment at clinic for 20 minutes.

Visit 6:

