Sample size was determined with reference to other studies that used similar endpoints. We assume that a standardized difference of 0.8 (the difference between groups divided by the standard deviation) is conservative to detect a clinically meaningful difference between groups (active RAVANS and sham). We will assume a type I error of 5% (alpha), a type 2 error of 10% (beta) and therefore the power will be 90%. Using the sample size calculation for a normal distributed population (t-test), 20 participants per arm will be necessary (total of 40 participants). Conservatively, we expect a 20% rate of dropout or loss to follow-up. We will assume that dropout participants will not improve from the last measured point; thus the sample size will be increased by 20% to 48 participants (24 per arm).

VII. RISK AND DISCOMFORTS

Blood Draws. Blood drawing may cause a small amount of pain. In addition, participants may get a temporary bruise or “black and blue mark”. Rarely, people faint when their blood is drawn. Very rarely, the vein may become red and swollen, or infected. If this occurs, we will treat the problem. Blood drawn will be performed by clinical phlebotomists to minimize the risk and discomforts.

Surveys/ Questionnaires. Some of the questions in the questionnaires may seem personal or embarrassing. Participants will be instructed that they may refuse to answer any of the questions that they do not wish to answer. If the questions make a participant very upset, we will help them to find a counselor. If participants develop fatigue during completing the questionnaire, we all ask the participant to take break.

RAVANS Risks: There is a small possibility of slight and temporary discomfort at the site where the electrodes are placed. Potential vaso-vagal reactions to stimulation

resulting in dizziness or light-headedness. The participant will be instructed to sit in chair while receiving RAVANS/Sham treatment.

The RAVANS procedure is without significant safety concerns. The electrical stimulator, checked by MGH Biomedical Engineering, has a current limiter preventing harmful stimulation levels.

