Uncommon Risks. Although we have made every effort to protect participant identity, there is a minimal risk of loss of confidentiality. Data collected from individuals will be kept confidential, accessible only to trained study staff. To protect against this risk, all participants will be assigned a study ID number and all collected data will be stored with this ID number and not include name or medical record number. A link between names and ID numbers will be kept separately under lock and key.

VIII. POTENTIAL BENEFITS

As with any study focusing on basic research, the subjects will derive no direct benefit. The noninvasive techniques and paradigms employed in the current proposal do not constitute any significant risk to the subjects. It is possible that the study participant will experience an improvement in fatigue, depression, anxiety, pain and cognitive function. We envision that in the near future the information obtained from the proposed research will provide a better understanding and treatment for subjects with PTLDS.

IX. MONITORING AND QUALITY ASSURANCE

Source of Research Material: Sources of materials to be collected include data from self-report fatigue, depression, anxiety, pain, and cognitive dysfunction from measurement scales, serum level of cytokines. All materials obtained are specifically for research purposes. The final dataset will include self-reported demographic, symptom data, serum level of cytokines. The final dataset will be stripped of identifiers prior to data analysis.

Data management. Each subject will have a file that includes consent form and all source data. All subject files will be kept at a locked cabinet at the Spaulding Rehabilitation Network Research Institute. Computerized data files will be protected by passwords to protect the confidentiality of the participants and the integrity of the data. Data management will be done by the Principal investigator, [name] and by the Clinical Research Coordinator.

Prior to being added as a co-investigator, the study staff member will be trained in RAVANS as well as all aspects of the evaluations. This study staff member will then be evaluated by the PI of the study. The PI will give confirmation that the co-investigator is qualified to do the evaluations and train the participant to use RAVANS.

The PI ([name]) who is a licensed physician must always be in the building at the time of each study session.

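### If anyone involved in enrolment can see earlier device modes, the printed block size of 4 makes an expected 16 of 48 assignments certain in advance

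*Combined protocol and SAP*

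**What the plan says.** - **Block size.** Section IV (Subject Enrollment) allocates "through a randomization approach with blocks of 4 (given the sample size of 48 participants, this would give 12 blocks of 4". It adds that "Randomization of subjects will be blocked based on the 2 treatment options available". No stratification factor is named, so there is one running sequence.
- **Ratio.** Section VI (Power analysis) gives the total: "thus the sample size will be increased by 20% to 48 participants (24 per arm". With equal arms, a block of 4 holds two active and two sham.
- **Disclosure of the arm.** Section V (Sham stimulation) states: "Participant will be given instruction to use Mode 1(Active RAVANS) or Mode 2 (Sham stimulation) according to randomization". It continues: "However, the participant would not know the setting of Mode 1 or Mode 2". No masking step is described for staff, although Section I calls the trial double-blind.
- **Who handles the device.** Treatment is given in the clinic and controlled from a tablet (Section V). Section IX describes co-investigators confirmed by the principal investigator as "qualified to do the evaluations and train the participant to use RAVANS".
- **Who enrols.** The investigator list gives one role "Principal Investigator, recruitment, screening and consenting, data collection and analysis". Section IV has that role review each phone screen before a visit is booked, and then obtain consent. Exclusion criterion 1 in Section III is left to judgement: "History of other neurological disorder that in the judgement of the investigator could interfere with the treatment or the interpretation of the results".
- **Not stated.** The protocol does not say who generates or holds the list, how an assignment is released, or at what moment in Visit 1 that happens.

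**The concern.** The issue is concealment of the next assignment. In a block of 4 with a 2:2 split, a person who knows the earlier modes in the block always knows the fourth assignment, and also knows the third when the first two match. The block size is printed in the protocol and the meaning of each mode is printed beside it, so earlier modes are the only other thing such a person needs.

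If that person also influences who is booked, excluded or encouraged to join, entry to the trial can depend on the coming arm. Masking the participant afterwards does not undo this. The main analysis in Section VI is an unadjusted unpaired t-test on change in a self-reported score, and the plan relies on the arms being alike at baseline. Nothing in that analysis would correct a difference created at entry.

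**Working it through.** **Inputs.** Block size 4 and 12 blocks (Section IV); two arms, no strata (Section IV); 48 participants, 24 per arm (Section VI). Assumption: the observer knows the block size and every earlier mode in the current block.

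**1. The plan's own figure.** 48 / 4 = 12 blocks with no remainder. It reproduces, and it leaves no room for another block size.

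**2. Assignments certain in advance.** Write A for active and S for sham. There are six equally likely orders. An assignment is certain once one arm has used both its places.

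| Order | Certain positions | Count |
|---|---|---|
| AASS, SSAA | 3 and 4 | 2 each |
| ASAS, ASSA, SAAS, SASA | 4 only | 1 each |

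Mean per block = (2×2 + 4×1)/6 = 4/3, which is 33.3% of 4. Over 12 blocks: 12 × 4/3 = **16 of 48**.

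This is an expectation. The count is 12 plus a binomial variable with 12 trials and probability 1/3, so its SD is √(12 × 1/3 × 2/3) = 1.6. The central 95% range is 13 to 19, and the limits are 12 and 24.

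**3. Best guess.** Guess the arm that is behind in the block, and toss a coin when level.

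- Position 1: 1/2
- Position 2: 2/3
- Position 3: 1/3 × 1 + 2/3 × 1/2 = 2/3
- Position 4: 1

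Mean = (0.5 + 0.667 + 0.667 + 1)/4 = **70.8%**, or 34 of 48, against 24 of 48 by chance.

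**4. What varying the block size achieves alone.** Lists of 48 were simulated. For the certainty column the observer knows the set of possible sizes but not their order.

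| Block sizes | Certain, of 48 | Best-guess success |
|---|---|---|
| 4 only | 16.0 | 70.8% |
| 4 or 6 | 2.8 | 69.0% |
| 4, 6 or 8 | 1.1 | about 68% (32.5 of 48) |

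Certainty nearly disappears, but predictability hardly moves. The running imbalance returns to zero at the end of every block, whatever its length. The arm that is behind is therefore always the better guess, and no knowledge of block size is needed to make it.

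**5. Possible effect on the primary comparison (illustration only).** The documents give no figure for selection, so a shift at entry is assumed: 0.25 SD of outcome towards the predicted arm, with no true effect.

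- Acting only on certain assignments: 2 × 0.25 × 1/3 = 0.17 SD spurious difference.
- Acting on every best guess: per block, correct minus wrong guesses average 1/3 + 1/3 + 1 = 5/3 of 4, so 2 × 0.25 × 5/12 = 0.21 SD.

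In simulation with 24 per arm, these raise the type I error from 5% to roughly 8% to 11%. At 0.1 SD it is about 6%; at 0.5 SD it is roughly 18% to 26%.

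**The case against.** The strongest reply is that block size is secondary. Prediction needs someone in enrolment to see unmasked earlier assignments. Without that knowledge, blocks of 4 reveal nothing; with it, varying blocks still leave about 68% of assignments guessable. This stands, and it is why changing the block size cannot be the whole remedy.

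It is also fair that the documents do not show the knowledge path. The sentence on the mode instruction is in the passive and names no role. Section IX requires the principal investigator only to be in the building during sessions. A reader might infer that the principal investigator sees the modes, or that 16 assignments will in fact be known. Neither is stated. Clinic delivery, the tablet control and the staff training text make it plausible that study staff see the modes, but it remains an inference.

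Two smaller replies also stand. Blocks of 4 are a recognised design, and only exclusion criterion 1 is expressly left to the investigator's judgement. In addition, Section V already lists consent, checklist, questionnaires, tests and blood draw before the first treatment. It does not say when the assignment is released, however, and late release protects only the current participant's entry and baseline. It does not stop the next assignment being predicted.

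**Conclusion.** The point holds as a conditional weakness with an inexpensive remedy. A single published block size, openly labelled modes, no described masking of staff and one role spanning recruitment to data collection together leave the next assignment open to prediction. If anyone involved in enrolment sees the earlier modes, an expected 16 of 48 assignments (range 12 to 24) are certain in advance and best-guess success is 70.8%. If no one does, the exposure by this route is zero.

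Two stronger readings should be avoided. The documents do not support saying that selection has occurred or that the primary result will be biased: guessability is calculated, whereas the size of any bias rests on an assumed shift. Nor does moving to varying blocks reduce the exposure from a third to about 2%. That describes certainty alone, and most of the predictability remains until earlier modes are hidden from enrolling staff.

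**What to change.** Make these changes together:

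1. **Blocks.** Replace the blocks-of-4 rule in Section IV with computer-generated permuted blocks of randomly varying size (for example 4, 6 and 8). Leave the sizes out of the protocol and all site documents.
2. **Coded modes.** Replace the Mode 1/active and Mode 2/sham labels in working documents with codes that enrolling staff cannot read. Participant-specific codes are safer than two fixed letters, because one unmasking would decode the whole list.
3. **List holder.** Have the list held by an existing team member who does not recruit, screen or assess, and name that role. State who operates the device. Active current is set to each person's thresholds while sham passes none, so the operator may learn the arm despite coding and should also be kept apart from enrolment.
4. **Release.** State that each assignment is released only after the eligibility checklist and all Visit 1 questionnaires, tests and blood draw are complete.

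The cost is a new list, a few protocol sentences and some separation of duties, with no added visits. If enrolment ends inside a block, the split may differ slightly from 24:24. With sizes up to 8 the worst case is 26:22 (22:22 after 44, then four in one arm).

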Fifteen mL of venous blood will be collected by vein for future measurement of serum biomarkers (IL-6, IL10, TNF, IL-1 β).

Questionnaires/ Surveys. A standard demographic survey and PTLDS symptoms will be collected using questionnaires outlined below.

1. Demographic Data Questionnaire (DDQ). A standard survey will be used to collect data including age, gender, racial background, marital status, education, employment and occupation, income.
2. Functional Comorbidity Index (FCI). Presence of chronic medical conditions will be measured using FCI which is a validated and reliable self-administered 18-item scale designed to examine the impact of comorbidities on physical function. Each participant will be asked to provide a list of prescription, over the counter, and recreational drugs used in the past 7 days.
3. Horowitz Lyme-Multiple Systemic Infectious Diseases Syndrome (HL-MSIDS) Questionnaire: This 55-item questionnaire evaluates the frequency, severity, and incidence of Lyme symptoms as well as assessing one's perceived overall health. A Likert scale from 0 - 3 (none – severe) is used to assess symptom frequency. The subsequent section assigns points to certain symptoms based on the answers in the first section. The third and fourth sections ask the subject to assign points to symptom incidence and health perception.
4. Sedentary Behaviors Questionnaire (SBQ): This 18-item questionnaire asks about the amount of time spent engaged in sedentary behaviors on typical weekdays and weekends.
5. Fatigue Symptom Inventory (FSI): This non-diagnosis-specific questionnaire measures the severity of fatigue symptoms and how much these factors interfere with the subjects' lives. There are 14 items, most of which are 0-10 point scales, one question asking about the amount of days fatigue is present, and another is a 0-4 scale on severity of fatigue. The higher the overall score correlates with more severe fatigue symptoms.
6. Brief Pain Inventory (BPI): This 15-item questionnaire assesses the location, severity, and type of current pain, using analogue scales and body diagrams.
7. Vulnerability questionnaire (VQ) This is a medical history questionnaire to ask about possible vulnerabilities to long-term neuroinflammation. Example questions include asking about the extent of previous use of antibiotics, opioids, anti-inflammatory steroids (e.g., prednisone), and previous exposure to pollutants and toxins.

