8. Beck Depression Inventory (BDI): This questionnaire evaluates current depressive symptoms. There are 21 items, each having four possible answers. Each item is scored between 0 and 3, with a higher score indicating greater symptom severity. The different items cover both psychological (e.g. concentration) and physical (e.g. appetite) symptoms of depression.

9. Beck Anxiety Inventory (BAI): This questionnaire evaluates current anxiety symptoms. There are 21 items, each having four possible answers. Each item is scored between 0 and 3, with a higher score indicating greater symptom severity. The different items cover both psychological (e.g. nervousness) and physical (e.g. hands trembling) symptoms of anxiety.
10. Pittsburgh Sleep Quality Index (PSQI): This 9-item questionnaire assesses sleep quality and patterns of sleep in adults over the past 30 days. It covers subjective sleep quality, latency, duration, habitual sleep efficiency, disturbances, use of sleeping medications, and daytime dysfunction due to poor sleep.

Objective Functional Tests. Participants will be asked to perform two functional tests; the Timed Up and Go (TUG) and the 4m usual walk speed. The Timed Up and Go test, and usual walk speed are commonly used objective tests of physical function, that independently predict poor outcomes in older adults. Minimal clinically important differences are 0.1 meters per second for gait speed, whereas a chair stand time of \geq 12 seconds predicts a 2.4-fold increased risk of falls in older adults.

Objectively measured Cognitive Function. We will use the NIH Toolbox Cognition Battery (NIHTB-CB) to assess cognitive function in participants with PTLDS. The NIHTB-CB is a computerized adaptive test that assesses several cognitive domains. It is administered by iPAD using the NIH Toolbox™ iPAD app. The following cognitive domains are assessed: executive function (inhibitory control/attention: Flanker Task; cognitive flexibility: Dimensional Change Card Sort), working memory (List Sorting), short-term memory (Picture Sequence), and an overall composite score that combines these outcomes (Fluid Cognition Composite).

Intervention:

RAVANS Procedures

The participant will be treated with RAVANS or sham at clinic for 20 minutes 3 times per week for 2 weeks.

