Subjects will receive RAVANS or sham treatment at clinic for 20 minutes. Subjects will complete the questionnaires (Horowitz Lyme-MSIDS, Sedentary Behaviors Questionnaire, Fatigue Symptom Inventory, Vulnerability Questionnaire, Brief Pain Inventory, Beck Depression Inventory, Beck Anxiety Inventory, Pittsburgh Sleep Quality Index), functional test (Timed Up and Go, 4 meter usually walking speed, NIH Toolbox cognitive battery), blood drawn for serum biomarkers (IL-6, IL-10, TNF, IL-1 β). Total visit times will be about 4 hours.

VI. BIOSTATISTICAL ANALYSIS

Our main outcome is to assess whether there is an improvement in symptoms (comparing before and after treatment) as indexed by HL-MSIDS score in the active RAVANS group as compared with sham. We chose the HL-MSIDS as the main outcome and therefore the other scale will be the secondary outcome. For the main analysis, we will compare the differences in HL-MSIDS changes between the two groups immediately after the end of treatment. We will therefore use an unpaired t-test for such analysis. Note here that we expect similar baseline level for both groups.

Besides this analysis, we will perform several exploratory analyses as listed below: we will compare the differences in changes in SBQ, FSI, BPI, BDI, BAI, PSQI, Timed- Up

and Go, 4m walk speed, NIHTB-CB, level of serum IL-6, IL-10, TNF, IL-1 β between the two groups immediately after the end of treatment. We will therefore use an unpaired t-test for such analysis.

Pearson correlation analysis will be applied to determine if serum level of biomarkers (IL-6, IL-10, TNF, IL-1 β) has correlation with symptom severity as index by HL-MSIDS, SBQ, FSI, BPI, BDI, BAI, PSQI, Timed- Up and Go, 4m walk speed, NIHTB-CB.

We will use the intention-to-treat analysis and do an analysis of only subjects that completed the 2-week study. For the intention-to-treat analysis, we will use a conservative method and assume that participants will not improve from the last measured point. The last-observation-carried-forward method will be appropriate because we expect no more than 10 percent of the observations were missing in each analysis.

Power analysis (e.g, sample size)

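### Outcomes after baseline are scheduled only at the sixth treatment session, and the plan specifies no way to obtain a score from someone who stops sessions early, so LOCF enters that person as zero change

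*Combined protocol and SAP*

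**What the plan says.** The intervention text in V. Study Procedures sets six sessions: "The participant will be treated with RAVANS or sham at clinic for 20 minutes 3 times per week for 2 weeks". The assessment table in that section marks HL-MSIDS, the other repeated questionnaires, the functional and cognitive tests and the blood draw at Visits 1 and 6 only. Visits 2-5 are treatment alone. The Visit 6 text joins the last session to the assessments: "Subjects will receive RAVANS or sham treatment at clinic for 20 minutes. Subjects will complete the questionnaires".

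On stopping, IV. Subject Enrollment says "Once enrolled, the subject may pause or terminate his/her participation at any time during the study". It does not separate ending sessions from leaving the study, and no assessment after early stopping is described.

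In VI. Biostatistical Analysis the main comparison is an unpaired t-test: "we will compare the differences in HL-MSIDS changes between the two groups immediately after the end of treatment". For intention-to-treat the plan will "assume that participants will not improve from the last measured point". It calls LOCF appropriate "because we expect no more than 10 percent of the observations were missing in each analysis". The other planned analysis is to "do an analysis of only subjects that completed the 2-week study". The power subsection of VI expects 20% dropout or loss to follow-up.

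**The concern.** With no HL-MSIDS between Visits 1 and 6, the last observation for anyone without a Visit 6 score is the baseline itself. LOCF therefore imposes a change of exactly zero. The completers analysis does not use the zeros, so it is a partial check, but it omits the same person. Neither planned analysis then holds a measured outcome for a stopper.

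Some stoppers may be willing to be assessed. For them the plan, followed as written, would put an assumed value into the primary comparison where a measured one could be had. An end-of-treatment score not taken at the time cannot be recovered by later analysis. If stoppers keep part of the effect, the zeros understate the difference. If stopping differs by arm while both arms improve, the zeros can bias the estimate either way.

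**Working it through.** **Inputs from the plan** (VI. Biostatistical Analysis, with its power subsection): 24 per arm, standardized difference 0.8, alpha 5%, 20% dropout, at most 10% missing. The plan does not state the sidedness; two-sided is assumed here.

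**Plan's own figures.** 20 × 1.2 = 24 per arm reproduces the inflation step. Power of 90% does not reproduce: at 0.8 SD, 24 per arm with complete data gives 77% by the two-sided t-test. That is a separate matter, but 77% is the reference point below.

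**Stoppers per arm.** 20% of 24 = 4.8, about 5 (5/24 = 20.8%). 10% of 24 = 2.4, so at most 2. Both cases are shown because the plan gives both rates.

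**Expected difference with zeros for k per arm:** 0.8 × (24 − k)/24.
- k = 5: 0.8 × 19/24 = 0.633 SD
- k = 2: 0.8 × 22/24 = 0.733 SD

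**If j of the k are assessed,** add e × j/24, where e is the effect stoppers keep (0, 0.4 or 0.8 SD). At k = 5:
- j = 1: 0.63, 0.65 or 0.67 SD
- j = 3: 0.63, 0.68 or 0.73 SD
- j = 5: 0.63, 0.72 or 0.80 SD

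**Power by simulation** (100,000 runs per scenario, normal changes with SD 1, fixed numbers of stoppers, two-sided 5% t-test). Sham improvement is an assumption, because the documents give none.

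| Sham improvement | 5 per arm, zeros | 2 per arm, zeros |
|---|---|---|
| 0 SD | 66% | 73% |
| 0.5 SD | 61% | 71% |
| 1 SD | 52% | 68% |

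With all stoppers assessed, and improving at least as much as sham, power runs from 55% (no effect kept) to 77-78% (all kept) at 5 per arm, and from 69% to 77-78% at 2 per arm. With 3 of 5 assessed it is 59-73%, 57-71% or 54-68% for the three sham values. If stoppers in both arms instead worsen by 0.5 SD on average (hypothetical), assessing all five gives about 51%, 45% or 36%, which is 14-16 points below the zeros. Completers only, 19 per arm: 67%.

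**No true effect, both arms improving by m SD.** Shift = (difference in number of stoppers)/24 × m.
- 5 v 5: 0/24 × m = 0; false positives 4.3% (m = 0.5) and 3.0% (m = 1)
- 7 v 3 (hypothetical), m = 0.5: 4/24 × 0.5 = 0.08 SD; 5.6%
- 7 v 3, m = 1: 4/24 × 1 = 0.17 SD; 7.0%
- 7 v 3, m = 1, with 4 of the 7 and 2 of the 3 assessed: (3 − 1)/24 = 0.08 SD; 5.0%

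**The case against.** The strongest reply has four parts.

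*The plan does not exclude stoppers from assessment.* This stands. A reader might infer that LOCF overrides the outcome even of someone willing to be assessed, but the text applies the rule to missing observations and nowhere withholds Visit 6 measures. Participants may pause, and someone who misses sessions but attends Visit 6 is measured. The gap is a missing procedure. It still matters, because collection is left to staff discretion and nothing says how such a score would be used.

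*Zero is a deliberate, disclosed and conservative choice.* Largely fair. With equal stopping it shrinks the difference and does not raise the false-positive rate. It is not conservative in general: if both arms improve and more sham participants stop, zeros favour RAVANS. A reader might infer that such bias is present, but the documents give no stopping rates by arm and nothing to support a 7 v 3 split.

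*At 10% missing the effect is small.* Also fair: 0.73 SD, with power of 68-73%. But the power subsection plans for 20%, where the plan's stated ground for LOCF no longer holds.

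*Assessment may not raise power.* Correct. It falls if stoppers keep little of the effect and sham improves little, and falls further if they worsen. Some stoppers will also be unreachable. The argument for assessment is that outcomes are measured, and it does not depend on a power gain.

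**Conclusion.** The point holds as a gap in the plan with a cheap remedy. No procedure obtains a score from an early stopper, so anyone without Visit 6 enters the primary analysis as exactly zero and is absent from the completers analysis. At the plan's own rates, zeros reduce a true 0.8 SD difference to about 0.63 SD (5 of 24 per arm) or 0.73 SD (2 of 24).

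The differences rest on the plan's 0.8 SD and equal stopping. The power figures also rest on an assumed sham improvement of 0 to 1 SD and normal changes with SD 1. How many stoppers could be assessed, and how they fare, is unknown. The documents therefore do not support saying that the trial is biased, that false positives are inflated, or that assessing stoppers would restore power.

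**What to change.** Amend V. Study Procedures so that every randomised participant who stops sessions, and does not withdraw consent to assessment, is asked to complete the Visit 6 assessments at about the date session 6 was scheduled for that person. No fixed study day is needed, since the protocol sets only the weekly frequency. If the full visit is refused, obtain HL-MSIDS alone (55 items). Leave timing unchanged for anyone who completes six sessions, including after a pause. Record the reason for stopping and the assessment date.

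Amend VI. Biostatistical Analysis so that the measured score is used in the intention-to-treat analysis and LOCF is kept only for scores that cannot be obtained. Participants keep the right to stop sessions, assessments or both.

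The cost is a short amendment and a few assessment-only visits of up to about 4 hours, or one questionnaire. About 5 per arm would be expected at 20% dropout; that is an expectation, not a maximum, and some will be unreachable. There are two downsides. Power may move either way. A stopper's score is also taken some days after the last session, so for that person it is not an immediate end-of-treatment measure.
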